8.10.6. Unscheduled Visit for a Grade 3 or Suspected Grade 4 Reaction

If a Grade 3 local reaction (Section 8.3.4.2), systemic event (Section 8.3.4.3), or fever (Section 8.3.4.4) is reported in the reactogenicity e-diary, a telephone contact should occur to ascertain further details and determine whether a site visit is clinically indicated. If a suspected Grade 4 local reaction (Section 8.3.4.2), systemic event (Section 8.3.4.3), or fever (Section 8.3.4.4) is reported in the reactogenicity e-diary, a telephone contact or site visit should occur to confirm whether the event meets the criteria for Grade 4.

A site visit must be scheduled as soon as possible to assess the participant unless any of the following is true:

- The participant is unable to attend the unscheduled visit.
- The local reaction/systemic event is no longer present at the time of the telephone contact.
- The participant or participant's parent(s)/legal guardian recorded an incorrect value in the reactogenicity e-diary (confirmation of a reactogenicity e-diary data entry error).
- The PI or authorized designee determined it was not needed.

This telephone contact will be recorded in the participant's source documentation and the CRF.

If the participant is unable to attend the unscheduled visit, or the PI or authorized designee determined that it was not needed, any ongoing local reactions/systemic events must be assessed at the next study visit.

8.10.7. COVID-19 and MIS-C Surveillance

If a participant experiences any of the following (irrespective of perceived etiology or clinical significance), he or she is instructed to contact the site immediately and, if confirmed, participate in an in-person or telehealth visit as soon as possible, optimally within 3 days of symptom onset (and at the latest 4 days after symptom resolution).

- A diagnosis of COVID-19;
- Fever:
- New or increased cough;
- New or increased shortness of breath;
- Chills;
- New or increased muscle pain;
- New loss of taste/smell;
- Sore throat;
- Diarrhea;
- Vomiting.

Note that:

- The CDC list of COVID-19 symptoms can be found at: https://www.cdc.gov/coronavirus/2019-ncov/symptoms-testing/symptoms.html.⁴² The additional symptoms listed by the CDC (ie, those not listed in the above protocol-defined list) should not trigger a potential COVID-19 illness visit unless, in the opinion of the PI, it is deemed necessary.
- If new symptoms are reported within 4 days after resolution of all previous symptoms, they will be considered as part of a single illness and a second illness visit is not required.
- Surveillance of potential COVID-19 symptoms should continue even if a participant has a positive SARS-CoV-2 test earlier in the study.

During the 7 days following each vaccination, potential COVID-19 symptoms that overlap with specific systemic events (ie, fever, chills, new or increased muscle pain, diarrhea, vomiting) should not trigger a potential COVID-19 illness visit unless, in the investigator's opinion, the clinical picture is more indicative of a possible COVID-19 illness than vaccine reactogenicity. If, in the investigator's opinion, the symptoms are considered more likely to

be vaccine reactogenicity, but a participant is required to demonstrate that he or she is SARS-CoV-2—negative, a local SARS-CoV-2 test may be performed: if positive, the symptoms should be recorded as a potential COVID-19 illness; if not, the symptoms that overlap with systemic reactogenicity events should be recorded in the reactogenicity e-diary or as AEs if not captured in the reactogenicity e-diary.

The participant or their parent(s)/legal guardian(s) are also instructed to contact the site immediately should the participant receive a positive SARS-CoV-2 test (NAAT or rapid antigen) result that is not accompanied by any symptoms. A potential COVID-19 visit is not required in this instance, but details of the positive test should be recorded in the designated CRF.

Participants may utilize a COVID-19 illness e-diary through an application (see Section 8.10.2) installed on a provisioned device or on the participant's or participant's parent(s)/legal guardian's own personal device to prompt him/her to report a diagnosis of COVID-19 or any symptoms of COVID-19. Note that this does not substitute for a participant's routine medical care. Therefore, participants should be encouraged to seek care, if appropriate, from their usual provider.

8.10.8. Potential COVID-19 Illness Visit (Optimally Within 3 Days After Potential COVID-19 Illness Onset)

This visit may be conducted as an in-person or telehealth visit; a telehealth visit involves the sharing of healthcare information and services via telecommunication technologies (eg, audio, video, video-conferencing software) remotely, thus allowing the participant, the participant's parent(s)/legal guardian, and investigator to communicate on aspects of clinical care.

As a participant's COVID-19 illness may evolve over time, several contacts may be required to obtain the following information:

- Record details of any of the prohibited medications specified in Section 6.9.1 received by the participant if required for his or her clinical care.
- Record AEs as described in Section 8.4. Note: Potential COVID-19 illnesses should not be recorded as AEs, with the exception of those assessed by the investigator as related to study intervention or those meeting the criteria for SAEs.
- If the visit is conducted in person, obtain a nasal (midturbinate) swab (collected by site staff). Alternatively, if conducted by telehealth, instruct the participant to self-collect a nasal (midturbinate) swab or instruct the participant's parent(s)/legal guardian to collect a nasal swab from their child at home and ship for assessment at the central laboratory.

- If the visit is conducted in person, obtain a blood sample (approximately 20 mL for participants ≥18 years of age and approximately 10 mL for participants 12 through 17 years of age), unless advised otherwise by Pfizer.
- Collect COVID-19—related standard-of-care clinical and laboratory information. This includes, but is not limited to:
 - Symptoms and signs, including
 - Clinical signs at rest indicative of severe systemic illness (RR ≥30 breaths per minute, HR ≥125 beats per minute, SpO₂ ≤93% on room air at sea level, or PaO₂/FiO₂ <300 mm Hg).
 - Evidence of shock (SBP <90 mm Hg, DBP <60 mm Hg or requiring vasopressors).
 - Significant acute renal, hepatic, or neurologic dysfunction.
 - Respiratory failure (defined as needing high-flow oxygen, noninvasive ventilation, mechanical ventilation, or ECMO).
 - Clinical diagnosis.
 - Any prescribed medication to treat or intended to treat COVID-19/MIS-C illness. Refer to Section 6.9.
 - Local laboratory SARS-CoV-2 test result(s). Note that if it is routine practice to perform a repeat local SARS-CoV-2 test for any reason, then a repeat nasal (midturbinate) swab should also be obtained and shipped for assessment at the central laboratory.
 - Full blood count.
 - Blood chemistry, specifically creatinine, urea, LFTs, and CRP.
 - Imaging results (eg, CT or MRI scan) to document neurologic dysfunction.
 - Number and type of any healthcare contact; duration of hospitalization and ICU stay.
 - Death.
- Complete the source documents.
- The investigator or an authorized designee completes the CRFs.

8.10.9. Potential COVID-19 Convalescent Visit (28 to 35 Days After Potential COVID-19 Illness Visit)

This visit is to be completed 28 to 35 days after all potential COVID-19 illness visits. A separate blood sample is needed for this visit for testing purposes even if it coincides with another visit. No convalescent visits should be conducted after Visit 5 (6-month follow-up visit).

- Collect/update COVID-19—related clinical and laboratory information (detailed in Section 8.10.8).
- Record details of any of the prohibited medications specified in Section 6.9.1 received by the participant if required for his or her clinical care.
- Record AEs as described in Section 8.4. Note: Potential COVID-19 illnesses should not be recorded as AEs, with the exception of those assessed by the investigator as related to study intervention or those meeting the criteria for SAEs.
- Collect a blood sample (approximately 20 mL for participants ≥18 years of age and approximately 10 mL for participants 12 through 17 years of age), unless advised otherwise by Pfizer.
- Complete the source documents.
- The investigator or an authorized designee completes the CRFs.

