8.2. Efficacy and/or Immunogenicity Assessments

8.2.1. Surveillance for COVID-19

Surveillance for potential cases of COVID-19 and MIS-C will occur throughout a participant's involvement in the study to describe both COVID-19 (all participants) and MIS-C (participants <21 years of age). If, at any time, a participant develops acute respiratory illness (see Section 8.10.7), for the purposes of the study he or she will be considered to potentially have COVID-19. In this circumstance, the participant or participant's parent(s)/legal guardian should contact the site, an in-person or telehealth visit should occur, and assessments should be conducted as specified in the SoA. The assessments will include a nasal (midturbinate) swab, which will be tested at a central laboratory using an RT-PCR test (Cepheid; FDA approved under EUA), or other equivalent nucleic acid amplification—based test (ie, NAAT), to detect SARS-CoV-2. In addition, clinical information and results from local standard-of-care tests (as detailed in Section 8.10.8) will be assessed. The central laboratory NAAT result will be used for the case definition, unless no result is available from the central laboratory, in which case a local NAAT result may be used if it was obtained using 1 of the following assays:

- Cepheid Xpert Xpress SARS-CoV-2
- Roche cobas SARS-CoV-2 real-time RT-PCR test (EUA200009/A001)
- Abbott Molecular/RealTime SARS-CoV-2 assay (EUA200023/A001)

Definitions of SARS-CoV-2—related cases, and SARS-CoV-2—related severe cases, will be considered as follows (for both, the onset date of the case will be the date that symptoms were first experienced by the participant; if new symptoms are reported within 4 days after resolution of all previous symptoms, they will be considered as part of a single illness):

- Confirmed COVID-19: presence of at least 1 of the following symptoms and SARS-CoV-2 NAAT positive during, or within 4 days before or after, the symptomatic period, either at the central laboratory or at a local testing facility (using an acceptable test):
 - Fever;
 - New or increased cough;
 - New or increased shortness of breath;

- o Chills;
- New or increased muscle pain;
- New loss of taste or smell;
- Sore throat;
- Diarrhea;
- Vomiting.

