8.4.7. Disease-Related Events and/or Disease-Related Outcomes Not Qualifying as AEs or SAEs

A potential COVID-19/MIS-C illness visit, potential COVID-19 illnesses, and their sequelae should not be recorded as AEs, with the exception of those assessed by the investigator as related to the study intervention or those meeting the criteria for SAEs. These data will be captured as efficacy assessment data only on the relevant pages of the CRF, as these are expected endpoints.

Through protocol amendment 2: Potential COVID-19 illnesses and their sequelae will not be reported according to the standard process for expedited reporting of SAEs, even though the event may meet the definition of an SAE. These events will be recorded on the COVID-19 illness pages in the participant's CRF within 1 day.

Note: However, if either of the following conditions applies, then the event must be recorded and reported as an SAE (instead of a DRE):

• The event is, in the investigator's opinion, of greater intensity, frequency, or duration than expected for the individual participant.

OR

• The investigator considers that there is a reasonable possibility that the event was related to study intervention.

Potential COVID-19 illness events and their sequelae will be reviewed by a group of internal case reviewers. Any SAE that is determined by the internal case reviewers NOT to meet endpoint criteria is reported back to the investigator site of incidence. The investigator must report the SAE to Pfizer Safety within 24 hours of being made aware that the SAE did not meet endpoint criteria. The investigator's SAE awareness date is the date on which the investigator site of incidence receives the SAE back from the internal case reviewers.

From protocol amendment 4: All SAEs occurring in a participant during the active collection period as described in Section 8.4.1 are reported to Pfizer Safety via PSSA or using the Vaccine SAE Report Form immediately upon awareness, and under no circumstance should this exceed 24 hours, as indicated in Appendix 3. This includes potential COVID-19 illnesses and their sequelae that meet the definition of an SAE.

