8.10.10. SARS-CoV-2 NAAT Results

Nasal (midturbinate) swabs for SARS-CoV-2 NAAT are obtained at:

- Visit 1: Contributes to the determination of a participant's baseline SARS-CoV-2 infection status.
- Potential COVID-19 illness visits: To determine whether symptoms experienced by the participant fulfill the COVID-19 case definition.

Through protocol amendment 2: Research laboratory—generated results from the illness visit swabs will be provided to the site once available, but this will not be in real time and cannot be relied upon to direct clinical care. Other research laboratory—generated results, including any positive vaccination visit swabs, will be provided to the site at the end of the study.

From protocol amendment 4: Research laboratory—generated results from the vaccination visit and illness visit swabs will be provided to the site at the end of the study only.

Therefore, the participant or participant's parent(s)/legal guardian should be directed to seek additional testing through the participant's primary healthcare provider at a licensed clinical laboratory when exhibiting potential COVID-19 symptoms or otherwise receiving a positive result and counseled on whether to take any precautionary measures pending confirmatory testing, as per local guidance.

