6.1.1.3. Adverse Events

6.1.1.3.1. Main Analysis

- Estimand: The percentage of participants reporting AEs from the study vaccination through 1 month after the study vaccination (Section 2.2).
- Analysis set: Safety population (Section 4).
- Analysis time point: From the study vaccination through 1 month after the study vaccination.
- Analysis methodology: Descriptive statistics (Section 5.2.1 and Section 3.1.1.4).
- Intercurrent events and missing data: Missing data will not be imputed except for partial AE start dates (Section 5.3).
- Reporting results: Counts, percentages, and the associated 2-sided Clopper-Pearson 95% CIs of AEs within 1 month after the study vaccination will be provided for each group.

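### Nonserious, unrelated illnesses with a COVID-19 symptom are kept off the AE page before testing, and no rule returns them if the NAAT is negative, so the primary 1-month AE percentage is understated

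*Protocol*

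**What the plan says.** **Entry to the illness pathway.** Protocol 8.10.7 tells the participant to contact the site on a COVID-19 diagnosis or any one of nine symptoms: fever, cough, shortness of breath, chills, muscle pain, loss of taste or smell, sore throat, diarrhea or vomiting. It applies if the participant "experiences any of the following (irrespective of perceived etiology or clinical significance". Protocol 8.2.1 says of a participant with such an illness that "for the purposes of the study he or she will be considered to potentially have COVID-19".

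**Recording.** Protocol 8.10.8 states "Potential COVID-19 illnesses should not be recorded as AEs, with the exception of those assessed by the investigator as related" to study intervention or meeting SAE criteria. Sections 8.4.7 and 8.10.9 carry the same rule. Section 8.4.7 adds: "These data will be captured as efficacy assessment data only on the relevant pages of the CRF, as these are expected endpoints".

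**Test results.** Under Protocol 8.10.10, illness-swab results went to sites when available, though not in real time, through amendment 2. From amendment 4, results from vaccination and illness "visit swabs will be provided to the site at the end of the study only".

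**Analysis.** The SAP 6.1.1.3.1 estimand is "The percentage of participants reporting AEs from the study vaccination through 1 month after the study vaccination". SAP 6.3.2 summarizes confirmed cases, severe cases and strain sequencing.

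**The concern.** The exclusion is written for potential illness, not confirmed illness, and none of the three sections makes it depend on the NAAT. Influenza or gastroenteritis in week 3 enters the pathway on symptoms alone. If it is nonserious and judged unrelated, it goes to the illness CRF pages. When the NAAT is negative, it is not a COVID-19 case either, so it appears in neither the AE tables nor the planned case summaries.

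AEs through 1 month are a primary safety endpoint in every cohort, and the objective is to describe the percentages themselves. Applying the same rule in all groups does not remove a downward bias in each of them. Several affected symptoms (fever, chills, muscle pain, diarrhea, vomiting) are also solicited reactogenicity events. Once the 7-day diary closes, their capture relies on AE reporting, which for these types then depends on a causality or seriousness judgement. Yet 10.3.1 defines an AE without regard to relatedness.

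**Working it through.** This is a recording rule, so the main check sets the sections side by side. Arithmetic is used only to illustrate size.

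**1. Is there a route back to the AE data after a negative NAAT?**

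| Provision | What it captures | What it leaves out |
|---|---|---|
| 8.4.7, 8.10.8, 8.10.9: exceptions | Illness judged related, or meeting SAE criteria | Nonserious, unrelated illness |
| 8.10.7: Days 1-7 | Fever, chills, muscle pain, diarrhea and vomiting judged to be reactogenicity trigger no illness visit. If a local test is done and is not positive, they go to the e-diary or AE page | Cough, sore throat, loss of taste or smell; everything after Day 7 |
| 8.4.7: internal case review, text headed through amendment 2 | "Any SAE that is determined by the internal case reviewers NOT to meet endpoint criteria is reported back to the investigator site of incidence" | Nonserious events |
| 8.10.11: work-up within 4 weeks (6 weeks from Cohort 4) | Diagnoses made after shortness of breath or other possible cardiac symptoms | The other listed symptoms, unless they suggest myocarditis or pericarditis |
| 8.10.9: convalescent visit | Updates clinical and laboratory information | Repeats the exclusion |
| SAP 3.1.1.4, 6.1.1.3.1, 6.1.1.3.2 | AEs recorded as such | No rule to add illness-CRF records |

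No row covers a nonserious, unrelated, NAAT-negative illness outside the Day 1-7 rule and the cardiac work-up.

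**2. Is such an illness an AE by the protocol's own definition?** Protocol 10.3.1 exempts the disease being studied and its expected course. A NAAT-negative illness does not meet the confirmed COVID-19 definition in 8.2.1. Section 8.4.1.2 requires all nonserious AEs in the active collection period to be recorded. Followed literally, the illness-visit rule therefore conflicts with 10.3.1 and 8.4.1.2.

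**3. The plan's nearest figure.** Protocol Table 8 uses 1 - (1 - p)^n. At p = 0.02 this gives 0.702, 0.867, 0.982 and 0.998 for n = 60, 100, 200 and 300, against the stated 0.70, 0.87, 0.98 and >0.99. All 36 cells reproduce. Table 8 is correct but cannot size this problem, because it takes complete recording for granted.

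**4. Illustration of size.** Let a be the recorded 1-month AE percentage and q the percentage of participants with an omitted illness. Neither is in the documents; both are assumed. If the two are independent, the percentage with those illnesses counted is 1 - (1 - a)(1 - q), the shortfall is q(1 - a), and the expected number of participants missed is n·q·(1 - a).

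| q | a = 5%: counted (shortfall, points) | a = 10%: counted (shortfall, points) | Missed at a = 5%: n = 60 / n = 300 |
|---|---|---|---|
| 1% | 5.95% (0.95) | 10.9% (0.9) | 0.57 / 2.85 |
| 2% | 6.9% (1.9) | 11.8% (1.8) | 1.14 / 5.7 |
| 5% | 9.75% (4.75) | 14.5% (4.5) | 2.85 / 14.25 |
| 10% | 14.5% (9.5) | 19.0% (9.0) | 5.7 / 28.5 |

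The group sizes are a Cohort 4 arm (60) and a combined Cohort 2 + 3 age group (300).

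**The case against.** The strongest reply is that the text is ambiguous rather than exclusionary. The illness-visit bullet opens by telling the site to record AEs under 8.4. Section 10.3.3 asks the investigator to seek a diagnosis and record that rather than symptoms. Section 8.4.7 rests its exemption on these being expected endpoints. An investigator who diagnoses influenza could reasonably decide that it is no longer a potential COVID-19 illness and record it. Nothing expressly forbids this. Under 10.3.3, an event of unknown cause is also handled as related for reporting purposes, which may widen the related exception. This stands as a reason not to claim that every such illness is lost, but it leaves the result to individual interpretation against a sentence saying the opposite.

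A reader might infer that sites cannot know the result. The documents do not support that in general: swab results were released during the study through amendment 2, participants with symptoms are directed to local testing, and local results and clinical diagnosis are collected at the illness visit. Release only at the end of the study begins with amendment 4. Even so, no section tells a site that has a negative result to move the event.

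It is also fair that the rule is the same in all groups, that the safety objectives are descriptive, and that an external committee reviews cumulative unblinded data. No hypothesis test depends on this percentage. This limits the consequence but leaves the percentage biased.

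**Conclusion.** The concern holds for a defined set of events: nonserious illnesses with a listed symptom, judged unrelated, NAAT-negative, and outside both the Day 1-7 reactogenicity rule and the cardiac work-up in 8.10.11. For these, the plan as written understates the primary 1-month AE percentage and conflicts with its own AE definition.

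Two stronger readings are tempting. One is that any illness with a listed symptom is kept off the AE page and never returned. The exceptions for related and serious events, the Day 1-7 rule, the SAE return route and 8.10.11 contradict that. The other is that capture of these event types is zero, so their detection probability in Table 8 falls to zero. That assumes what has to be shown, since investigators are not barred from recording another diagnosis.

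The size is unknown. The range of about 1 to 9.5 points rests on an assumed illness rate of 1% to 10%, an assumed recorded AE percentage of 5%, independence between the two, and the exclusion being followed literally.

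**What to change.** **Protocol.** In 8.4.7, 8.10.8 and 8.10.9, limit the exemption to illnesses meeting the confirmed COVID-19 definition in 8.2.1. Reconcile the remaining illness-CRF records with the AE data once NAAT results can be released to sites, so that the investigator supplies the causality assessment required by 10.3.3. The sponsor should not map single records into the main AE table, which would bypass that assessment. Earlier queries confined to NAAT-negative cases should also be avoided, since they would reveal results that 8.10.10 withholds.

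**SAP.** In 6.1.1.3.2, add for every cohort a supplemental 1-month AE summary that also includes illness-CRF records with onset through Visit 3 that do not meet the confirmed definition, using the recorded clinical diagnosis and onset date. Show illnesses without a NAAT result separately, because some will be true COVID-19. From amendment 4, reconciliation with sites has to wait for the end of the study, so this summary is what would inform the Visit 3 analysis in SAP 7.3.

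**Cost.** Wording changes, some extra programming and a late reconciliation step, all on data already collected, with no new participant procedure. Reported AE percentages will be slightly higher.
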